## 4. STUDY DESIGN

This is a prospective, randomized, controlled, multi-center clinical trial to evaluate the effectiveness and safety of the NW System for the treatment of nightmare disorder secondary to post-traumatic stress disorder.

### 4.1. Treatment Assignment

Any subject meeting all inclusion and no exclusion criteria is eligible for enrollment in the study. Subjects are considered enrolled in the study once the informed consent form (ICF) and Health Insurance Portability and Accountability Act (HIPAA) form have been executed.

All subjects will receive a NW System (research phone, research watch, and NW proprietary application-set to either an active mode or a sham mode). 240 subjects will be enrolled into the study. Subjects will be randomly assigned to receive either the Active System or Sham System. There will be 120 subjects in each arm. None of the subjects will be aware of whether they have received an Active System or a Sham System. For further details of treatment assignment procedures, go to the “Randomization” section of this protocol.

## 5. STUDY POPULATION

Veterans and active-duty service members that meet the inclusion and exclusion criteria will be enrolled in the study.

### 5.1. Inclusion Criteria

#### Inclusion Criteria

- Either Diagnosis of PTSD via American Psychiatric Association PTSD diagnostic criteria in the fifth edition of its Diagnostic and Statistical Manual of Mental Disorders (DSM-5) or having symptoms consistent with PTSD (subject must score at least 25 on the PTSD Checklist-5 to qualify for the study).
- Equal to or older than 22 years of age.
- Proficient in both reading and writing in the English language.
- Pittsburgh Sleep Quality Index (PSQI). Potential participants would need to score 10 or more to qualify.
- ESS: On question #8 any score above “0” will prompt an additional question:
  - Do you drive (“get behind the wheel”) when you are drowsy?
    - Answer must be “No” to be enrolled in the study due to safety concerns.
- Have repetitive nightmares contributing to disrupted sleep as reported by the subject
- Wireless Internet and two power outlets where they sleep
- Prazosin use; if yes, subject may be included if willing to be tapered by prescribing provider.
  - Taper must be completed, and the subject must be off prazosin for 2 weeks prior to enrollment.
- Alpha blocker use; if yes, subject may be included if willing to be tapered by prescribing provider. Taper must be completed, and the subject must be off all alpha blockers for 2 weeks prior to enrollment.

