## 5.2. Exclusion Criteria

- Patient Health Questionnaire-9 (PHQ-9) score greater than or equal to 20 indicates that the subject is too depressed to be included in this study.
  - Score of 1 or more on the suicide ideation item (question #9) of the PHQ-9 will trigger a risk assessment by the principal investigator or qualified co-investigator.
- Responses on the C-SSRS that indicate High Suicide Risk.
  - Study staff will contact a licensed Behavioral Health Provider to assess any subject who reports any symptoms that fall into the High-Risk categories or are having current (within the last month) suicidal ideation.
- Uncontrolled atrial fibrillation
- Current use of varenicline
- Current use of beta-blockers (unless ophthalmic solutions). See “Excluded Medications List” in Appendix A.
- Current use of non-dihydropyridines. See “Excluded Medications List” in Appendix A.
- Current use of Prazosin for the treatment of nightmares (can include subjects 2 weeks post-taper and discontinuation). This would be coordinated with the prescribing provider.
- Current use of alpha blockers (can include subjects 2 weeks post-taper and discontinuation under guidance from prescribing provider).
- Circadian rhythm disruption on a regular basis (shift work)
  - Including regularly scheduled overnight care of very young, elderly, or sickly family members
- Known diagnosis of OSA
- Diagnosis of an active disorder of arousal from non-rapid eye movement sleep
- Diagnosis of rapid eye movement sleep behavior disorder
- Diagnosis of narcolepsy
- Alcohol Use Disorders Inventory Test (AUDIT) (score equal to 8 or higher)
- Drug Abuse Screening Test-10 (DAST-10) (score greater than 2)
- Suspicion of nightmares being secondary to substance abuse or withdrawal
- Diagnosis or suspicion of dementia
- Previous or foreseeable legal proceedings involving nightmares or trauma
- Nocturia that causes awakening from sleep
- Known sleep walking
- Wrist tattoos on the both arms where the watch will be worn, that prevent detection of heart rate by the device watch.

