**6.4. Enrollment: Visit 1, Day 0**

Those who pass the telephone pre-screening will be scheduled for an Enrollment Visit (Visit 1, Day 0).

Procedures to be done at this visit include:

1. Re-check of inclusion/exclusion criteria prior to signing enrollment forms.
2. Signing of Informed Consent Form (ICF) and HIPAA
3. Completion of a Demographics Form
4. Baseline Psychometric Instruments:
  - a. Pittsburgh Sleep Quality Index (PSQI)
  - b. PSQI Addendum for PTSD (PSQI-A)
  - c. PCL-5 Checklist (past 1 month)
  - d. Clinician-Administered PTSD Scale for DSM-5 (CAPS-5)
  - e. Patient Health Questionnaire-9 past 1-month version (PHQ-9) (Score greater than or equal to 20 indicates severity of depression too great for this study. Score of 1 or more on the suicide ideation item [question #9] to trigger a risk assessment by PI and a licensed Behavioral Health Provider.)
  - f. Epworth Sleepiness Scale ESS: On question #8 any score above “0” will prompt an additional question:
    1. Do you drive (“get behind the wheel”) when you are drowsy?
      - a. Answer must be “No” to be enrolled in the study due to safety concerns.
  - g. DAST-10: Exclude if score is greater than two (2).
  - h. AUDIT: Exclude if score is equal to, or greater than, eight (8).
  - i. Functional Outcomes of Sleep Questionnaire (FOSQ)
  - j. Insomnia Severity index (ISI)
  - k. Trauma Related Nightmare Scale (TRNS)

- l. VR-12 Quality of Life (VR-12)
- m. NW Likert Scale for Sleep Quality (NW Likert) 7-day
- n. Columbia-Suicidality Severity Rating Scale, Lifetime and Recent version (C-SSRS) (responses in the High-Risk range will make the subject ineligible).
  - i. After further assessment with the PI, Study Staff will contact the healthcare provider that has been trained to perform a suicide assessment for all subjects with a rating greater than “LOW”.
- o. RedCAP collection questionnaire: What type or types of traumas led to your PTSD? (Choose the primary type of trauma that applies) 1) Combat/blast trauma 2) Sexual Trauma/Rape/Sexual Assault 3) Natural Disaster 4) Childhood physical abuse 5) Accident, such as a car accident 6) Other (a secondary choice would appear for free text).
5. Baseline health assessments

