### **2. Psychometric Instruments:**

- a. Pittsburgh Sleep Quality Index (PSQI)
- b. PSQI Addendum for PTSD (PSQI-A)
- c. PCL-5
- d. Insomnia Severity Index (ISI)
- e. (PHQ-9) (Score of 1 or more on the suicide ideation item [question #9] to trigger a risk assessment by a licensed Behavioral Health Provider if deemed necessary by the PI.)
- f. Epworth Sleepiness Scale ESS
- g. Functional Outcomes of Sleep Questionnaire (FOSQ)
- h. Trauma Related Nightmare Scale (TRNS)
- i. VR-12 Quality of Life (VR-12)
- j. NW Likert Scale for Sleep Quality (NW Likert)
- k. Columbia-Suicidality Severity Rating Scale, Since Last Contact version (C-SSRS)
  - i. If deemed necessary by the PI, Study Staff will contact a healthcare provider that has been trained to perform a suicide assessment if there is any risk of suicide.
- l. Blinding Assessment Questionnaire

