### **6.13. Day 60: Visit 3 – Patient Questionnaire Assessment**

Participants will complete questionnaires on Day 60 (+7 days). Study coordinator will contact participants on Day 62 and after if the questionnaires have not yet been not completed.

Procedures to be done during the call: Questionnaires to be completed:

1. Psychometric Instruments:
  - a. Pittsburgh Sleep Quality Index (PSQI)
  - b. PCL-5
  - c. (PHQ-9) (Score of 1 or more on the suicide ideation item [question #9] to trigger a risk assessment by the PI, and if necessary, a licensed Behavioral Health Provider.)
  - d. Epworth Sleepiness Scale ESS
  - e. Trauma Related Nightmare Scale (TRNS)
  - f. Insomnia Severity index (ISI)
  - g. VR-12 Quality of Life (VR-12)
  - h. NW Likert Scale for Sleep Quality (NW Likert)
  - i. Columbia-Suicidality Severity Rating Scale, Since Last Contact version (C-SSRS)
    - i. Study Staff will immediately contact the PI, and if necessary, a healthcare provider that has been trained to perform a suicide assessment if there is any risk of suicide.

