### **6.14. Day 90: Visit 4 – Patient Questionnaire Assessment**

Participants will complete questionnaires on Day 90 (+7 days). The study staff will contact participants on Day 92 and after if the questionnaires have not yet been completed. When all questionnaires are completed, the study staff will call or text the participants to confirm that their involvement in the study is complete and to reiterate the instructions on returning the study device.

Questionnaires to be completed:

Health assessments

1. Psychometric Instruments:
  - a. Pittsburgh Sleep Quality Index (PSQI)
  - b. PCL-5
  - c. Insomnia Severity index (ISI)
  - d. (PHQ-9) (Score of 1 or more on the suicide ideation item [question #9] to trigger a risk assessment by the PI, and if necessary, a licensed Behavioral Health Provider.)
  - e. Epworth Sleepiness Scale ESS
  - f. Trauma Related Nightmare Scale (TRNS)

- g. VR-12 Quality of Life (VR-12)
- h. NW Likert Scale for Sleep Quality (NW Likert)
- i. Columbia-Suicidality Severity Rating Scale, Since Last Contact version (C-SSRS)
  - i. Study Staff will immediately contact the PI, and if necessary, a healthcare provider that has been trained to perform a suicide assessment if there is any risk of suicide.

Subjects will be allowed to keep the device at the end of the study, but will be given a \$100 reimbursement if they return it. The device can only be used for NightWare. No other applications are enabled on the device.

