## **9. Safety**

### **9.1. Risk/Benefit Assessment**

#### **9.1.1. Known Potential Risks**

There are no predicate devices used specifically to treat nightmares. However, there are many variations of over-the-counter applications and wearable devices that vibrate to signal the wearer. The same risks known to over-the-counter wearable fitness devices apply to this device.

The NW digital therapeutic is designed to interrupt during a nightmare, but not awaken the individual. The device may instead awaken, or incorrectly diagnose a nightmare and alarm (false positive). Therefore, worsening sleep quality is a potential risk of this device intervention.

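### Optional low-cost safety addition: the drowsy-driving question that bars entry is not carried forward to the Day 30, 60 and 90 sleepiness assessments

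*Protocol*

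**What the plan says.** Protocol 5.1 makes the drowsy-driving question conditional on ESS item 8. A participant who scores above 0 on that item must answer No "to be enrolled in the study due to safety concerns". The Visit 1 procedures repeat the rule in 6.4 item f ("Epworth Sleepiness Scale ESS: On question #8 any score above" zero leads to the driving question).

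The Schedule of Activities (1.3) marks the ESS at Visits 1, 2, 3 and 4. The follow-up visit lists name the instrument and nothing more:

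- 6.12, Day 30: "f. Epworth Sleepiness Scale ESS"
- 6.13, Day 60: "d. Epworth Sleepiness Scale ESS"
- 6.14, Day 90: "e. Epworth Sleepiness Scale ESS"

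The same three lists do attach individual actions to other instruments. At Day 60, a score of 1 or more on PHQ-9 item 9 is "to trigger a risk assessment by the PI, and if necessary, a licensed Behavioral Health Provider". The C-SSRS entries also carry an escalation step.

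Section 9.1.1 states that "worsening sleep quality is a potential risk of this device intervention". Section 7.5 of the Protocol and the Primary Safety Analyses section of the SAP make daytime sleepiness on the ESS the primary safety endpoint. It is tested as mean change from baseline to Day 30 in the Active arm.

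**The concern.** The driving question is one of the few entry criteria that the protocol justifies explicitly by safety, and it concerns a hazard that the device could plausibly affect. By the protocol's own account, the watch may wake the user or vibrate when there is no nightmare, and poorer sleep may follow. A participant could pass entry, become sleepier on active treatment and then drive while drowsy. That person would meet the condition that would have barred them before exposure, yet the protocol text requires nobody to ask. Sham participants are in the same position once they cross over to active treatment at Visit 2.

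The planned ESS test does not fill this gap. It compares a group mean with baseline, so a stable mean can hide individuals who worsen, and its result prompts no action for any one participant. What is at stake is individual safety. The efficacy comparison and its power are not affected.

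**Working it through.** The plan gives no figure on this point, so the check is a comparison of the visit lists followed by a count of forms.

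**Step 1: where the prompt and an individual action appear.**

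| Assessment | ESS given | Item 8 prompt and driving question | Individual action on the ESS | Action on PHQ-9 item 9 and C-SSRS |
|---|---|---|---|---|
| Day 0 (5.1, 5.2, 6.4) | Yes | Yes | Yes bars entry | Yes |
| Day 30 (6.12 e, f, k) | Yes | Not specified | Not specified | Yes |
| Day 60 (6.13 c, d, i) | Yes | Not specified | Not specified | Yes |
| Day 90 (6.14 d, e, i) | Yes | Not specified | Not specified | Yes |

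The question is specified at 1 of 4 administrations, and at 0 of 3 after Day 0. Section 9.1.3 shows the same contrast: it gives escalation steps for the C-SSRS and lists the ESS without any.

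**Step 2: whether another safeguard already asks.** The protocol describes:

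- remote monitoring with adjustment of threshold and strength (2.2, 2.3)
- prompt reporting of phone or watch problems (6.4 item 11)
- a daily questionnaire on sleep quality, device disruption and nightmare awakenings (6.6)
- help calls as needed, and calls on Days 7 and 21 (6.8, 6.9, 6.11)
- withdrawal at investigator discretion (8.1)
- freedom to stop wearing the watch (9.1.3)
- adverse event reporting (9.2.4)

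These act on disturbed sleep, device function or reported events. None, as described, asks about driving.

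**Step 3: how many forms could carry the question.** Inputs: 120 participants per arm (4.1), or 60 completers per arm (7.3) who are assumed to stay to Day 90. Active participants have three ESS forms after active exposure (Days 30, 60, 90). Sham participants have two (Days 60, 90), because they cross over at Visit 2 (1.3).

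| Quantity | Formula | 120 per arm | 60 per arm |
|---|---|---|---|
| Forms after active exposure | 3n + 2n | 360 + 240 = 600 | 180 + 120 = 300 |
| Of these, participation can still change (Active Day 30, both arms Day 60) | n + 2n | 120 + 240 = 360 | 60 + 120 = 180 |
| Of these, Day 90, counselling only | 2n | 240 | 120 |
| Sham Day 30, before active exposure, asked to keep the arms alike | n | 120 | 60 |

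Check: 360 + 240 = 600, and 180 + 120 = 300.

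The first column is a ceiling. The 240 are counted at consent (7.3), and a consented person can still fail eligibility before randomization (6.4 item 6). The question is put only when item 8 exceeds 0, and the documents do not give that share.

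**The case against.** The strongest reply is that nothing here is inconsistent. The driving question is an eligibility criterion, and nothing in the protocol says it governs continuation. Other entry cutoffs are not carried forward either: a PHQ-9 total of 20 or more "indicates that the subject is too depressed to be included in this study", and no later section acts on that total. A reader might infer that the protocol breaks its own safety rule after Day 0, or that a later Yes should mean withdrawal. The documents support neither reading.

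The comparison with the PHQ-9 is also imperfect. At Day 14 (6.10) the PHQ-9 is listed with no item 9 trigger, so silence in a visit list is weak evidence of a deliberate omission. The C-SSRS steps address what 9.1.3 treats as imminent danger, and self-reported driving is not classed that way. The link from worse sleep to driving is inferred, since neither 9.1.1 nor 7.5 mentions driving.

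A reader might further infer that nobody asks about driving during the trial. That goes too far. The Help Calls questionnaire, the REDCap forms, the Home Instruction Sheet and the consent pages are not among the documents and may cover it.

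Finally, a reader might take a follow-up Yes as new and caused by the device. It need not be. Participants who scored 0 on item 8 at entry were never asked about driving, so their Yes may describe an old habit.

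All of this stands, and it limits the point to an optional addition. It does not remove the observation that a stated safety bar, on a matter tied to a named device risk and to the primary safety endpoint, has no follow-up in the protocol text.

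**Conclusion.** The point holds as an optional, low-cost safety improvement, with medium confidence. The protocol text specifies the driving question at Day 0 only and attaches no individual action to the ESS at Days 30, 60 or 90. The reach is at most 600 post-exposure forms, of which 360 could still affect participation (300 and 180 with 60 completers per arm). These figures describe opportunities to ask. It would be wrong to read them as participants at risk, because the documents give neither a rate of drowsy driving nor the share scoring above 0 on item 8.

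The conclusion rests on two assumptions: that the visit lists in 6.12 to 6.14 are complete as to ESS procedures, and that no document outside the protocol and SAP already asks. If one does, a cross-reference in those sections is enough. Sample size, power and the efficacy test are unaffected.

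**What to change.** Add to the ESS line in 6.12, 6.13 and 6.14, for both arms: *If question 8 scores above 0, ask the driving question as worded in 5.1. Pass any Yes promptly to the PI for safety counselling and, at Days 30 and 60, a decision on continued participation.*

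At Day 30 the PI should act only after all Visit 2 questionnaires, including the Blinding Assessment (6.12 item l), are complete. The Day 30 PSQI and the blinding answers are then recorded before any intervention. Asking both arms the same question keeps the procedure identical across arms.

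If Day 30 answers are tabulated by arm, present them as a descriptive safety row without a test. Add a note that a Yes need not be new, because those scoring 0 on item 8 at entry were not asked.

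The cost is one conditional question on a form already collected, a line in each of three sections, and occasional PI contacts. It also needs a protocol amendment with IRB review and approval before use, and a decision on re-consent if the consent form changes (section 15).

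There are two limits. The ESS is not given between Day 0 and Day 30, so the change detects nothing earlier, although active treatment starts at about Days 2 to 3 (6.6). At Day 90 it serves counselling only, because study involvement ends; that still has some value, since participants may keep the device (6.14).

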## 5.2. Exclusion Criteria

- Patient Health Questionnaire-9 (PHQ-9) score greater than or equal to 20 indicates that the subject is too depressed to be included in this study.
  - Score of 1 or more on the suicide ideation item (question #9) of the PHQ-9 will trigger a risk assessment by the principal investigator or qualified co-investigator.
- Responses on the C-SSRS that indicate High Suicide Risk.
  - Study staff will contact a licensed Behavioral Health Provider to assess any subject who reports any symptoms that fall into the High-Risk categories or are having current (within the last month) suicidal ideation.
- Uncontrolled atrial fibrillation
- Current use of varenicline
- Current use of beta-blockers (unless ophthalmic solutions). See “Excluded Medications List” in Appendix A.
- Current use of non-dihydropyridines. See “Excluded Medications List” in Appendix A.
- Current use of Prazosin for the treatment of nightmares (can include subjects 2 weeks post-taper and discontinuation). This would be coordinated with the prescribing provider.
- Current use of alpha blockers (can include subjects 2 weeks post-taper and discontinuation under guidance from prescribing provider).
- Circadian rhythm disruption on a regular basis (shift work)
  - Including regularly scheduled overnight care of very young, elderly, or sickly family members
- Known diagnosis of OSA
- Diagnosis of an active disorder of arousal from non-rapid eye movement sleep
- Diagnosis of rapid eye movement sleep behavior disorder
- Diagnosis of narcolepsy
- Alcohol Use Disorders Inventory Test (AUDIT) (score equal to 8 or higher)
- Drug Abuse Screening Test-10 (DAST-10) (score greater than 2)
- Suspicion of nightmares being secondary to substance abuse or withdrawal
- Diagnosis or suspicion of dementia
- Previous or foreseeable legal proceedings involving nightmares or trauma
- Nocturia that causes awakening from sleep
- Known sleep walking
- Wrist tattoos on the both arms where the watch will be worn, that prevent detection of heart rate by the device watch.

## 5.3. Screen Failures

Subjects that are screened but do not meet inclusion or exclusion criteria will not be enrolled or followed in the trial. Screen failures will be informed of other possible treatments available. Persons that failed screening due to Suicidal Ideation or having Moderate- to High-Risk on the C-SSRS will be assessed by the PI and, if deemed necessary, referred to a qualified Behavioral Health Provider immediately and provided appropriate referrals for emergency or outpatient treatment as indicated by risk assessment.

## **6. STUDY METHODS**

### **6.1. Pre-recruitment**

We will request a HIPAA Waiver and a Waiver of the Informed Consent Form (ICF) for purposes of recruitment. Note that no participants will be enrolled in the study without full written consent. The HIPAA Waiver will allow us to request that a computer search be done so that veterans and active-duty service members who meet the basic inclusion/exclusion criteria can be found. The Waiver of Informed Consent will also allow us to call and speak to the possible subject and to conduct a phone screen.

### **6.2. Recruitment**

1. Subjects will be recruited using fliers and referrals from areas like the PTSD Clinic, VA Hospital CBOCs, Non Clinical counseling veteran centers, and mental health and behavior health clinics. Invitation letters will be sent to all veterans and active-duty service members compiled from the computer search, asking them to call the study coordinator if they are interested in study participation.
2. If the subject has not contacted study staff within two weeks after the recruitment letter is mailed, the subject may be called and/or texted by study staff.
  - a. Study Staff has requested a IRB-Approved Cell Phone to assist in contacting and interacting with potential/enrolled subjects. (See Cell Phone/Text message content document submitted with this protocol).
3. Recruitment letters/Fliers will specify that if the veteran calls and either speaks to study staff or leaves a voicemail (secured) expressing interest, that their medical charts will be checked to determine eligibility.
4. If study staff answer the phone when the veteran calls, the veteran will be told about the study requirements and, if interested, phone screened.
5. Based on the phone screen results, those veterans and active-duty service members who appear to qualify will be told that their chart will be checked to make the final determination of their eligibility.
6. Study staff will call and/or text veterans and active-duty service members who leave messages after their chart has been checked for inclusion/exclusion criteria. If the veteran and active-duty service member appears to qualify, the phone screen will be conducted, and the veteran and active-duty service member will know his/her eligibility at the end of the call.
7. Veterans and active-duty service members that pass both chart review and phone screening will be invited to come in for an enrollment visit.
8. Veterans and active-duty service members and active-duty service members who do not qualify for the study will be told of other treatment options. These options are on the Handout "Post-Study Resources for Participants". Contents of Handout may be read to the veteran and active-duty service member over the phone and/or the Handout mailed to the veteran and active-duty service member as requested.

